Study Protocol and Statistical Analysis Plan

Official Title:

Evaluation of Observation Periods and Biphasic Reaction Risk Factors in Pediatric Anaphylaxis Cases in the Pediatric Emergency Department: A Retrospective Study

Brief Title:

Observation Periods and Biphasic Reaction Risk Factors in Pediatric Emergency Anaphylaxis Cases

Unique Protocol ID:

ADUPEDANAPH

NCT Number:**Responsible Party / Principal Investigator:**

Assoc. [name]. [name]

Department of Pediatrics (Emergency and Intensive Care)

Adnan Menderes University Faculty of Medicine, Aydın, Turkey

Co-Investigators:

- Dr. Öğr. Üyesi [name]
- Dr. Öğr. Üyesi [name]
- Uzm. [name] [name]

Ethics Approval:

Approved by the Clinical Research Ethics Committee of Adnan Menderes University Faculty of Medicine (Approval Date: 24/09/2025).

Document Date: 03 October 2025

1. Study Rationale

Anaphylaxis is a severe, rapidly developing systemic allergic reaction that poses unique challenges in pediatric emergency care. International guidelines recommend observation after treatment due to the risk of biphasic reactions (recurrence within 1–72 hours), but the optimal observation period in children is uncertain. Limited data exist from Turkey regarding pediatric anaphylaxis triggers, treatment practices, biphasic reaction frequency, and risk factors.

2. Objectives

- **Primary Objective:**

To determine the average observation period in the pediatric emergency department for children presenting with anaphylaxis and to evaluate the frequency and timing of biphasic reactions.

- **Secondary Objectives:**

- To analyze independent risk factors for biphasic reactions, including delayed epinephrine administration, asthma history, and severity at presentation.
- To assess the rate of hospital admission and need for intensive care.
- To describe treatment patterns (use and timing of epinephrine, corticosteroids, antihistamines, fluids) in the emergency setting.

3. Hypotheses

H1: Early administration of intramuscular epinephrine reduces the risk of biphasic reactions and improves clinical outcomes.

H2: A history of asthma and severe initial clinical presentation are associated with higher risk of biphasic reactions and prolonged observation requirements.

H3: Children requiring multiple doses of epinephrine are at increased risk for hospitalization and biphasic reactions.

4. Study Design

Type: Observational

Design: Retrospective analytic cohort (chart review)

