Setting: Pediatric Emergency Department, Adnan Menderes University Hospital

Period: January 1, 2014 – December 31, 2024

Sample: All consecutive patients <18 years diagnosed with anaphylaxis

5. Study Population

Inclusion Criteria:

- Children aged 0–18 years
- Diagnosis of anaphylaxis according to WAO 2020 criteria
- Complete medical records available

Exclusion Criteria:

- Incomplete or missing medical records

- Cases not meeting WAO 2020 diagnostic definition
- Isolated urticaria or localized allergic reactions

6. Methods

Data Sources: Patient files and electronic medical records (January 2014 – December 2024).

Variables collected:

- Demographics (age, sex)
- Medical history (comorbidities such as asthma, allergic diseases)
- Triggers (food, drug, insect sting, idiopathic)
- Clinical manifestations (skin, respiratory, cardiovascular, gastrointestinal, neurological)
- Treatments (IM epinephrine, time to first dose, number of doses, IV antihistamines, IV corticosteroids, fluid therapy, inhaled therapy)
- Duration of ED observation, hospitalization, ICU stay
- Occurrence and timing of biphasic reactions
- Outcomes: discharge, readmission, mortality (if any)

7. Statistical Analysis Plan

- **Software:** SPSS v20.0
- **Descriptive statistics:** Continuous variables will first be tested for normality (e.g., Shapiro-Wilk test). Normally distributed variables will be presented as mean \pm SD, while non-normally distributed variables will be expressed as median (IQR). Categorical variables will be summarized as n (%).
- **Comparisons:** Chi-square or Fisher's exact test for categorical variables; Student's t-test or Mann-Whitney U test for continuous variables, depending on distribution.
- **Regression analysis:** Logistic regression to identify independent predictors of biphasic reactions and prolonged observation (candidate variables: time to epinephrine, asthma, severity, multiple epinephrine doses).
- **Significance level:** $p < 0.05$ considered statistically significant.

Sample size: All eligible patients.

8. Ethical Considerations

- Approved by Adnan Menderes University Faculty of Medicine Clinical Research Ethics Committee (Approval No: 2025/266).

- Retrospective study design → no informed consent required.
- All data anonymized and stored securely.

9. Expected Contribution

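### Time to first epinephrine dose has no time origin, and no symptom-onset time, ED arrival time or pre-arrival dose is collected, so H1 may not be tested on the delay it refers to

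*Combined protocol and SAP*

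**What the plan says.** Three parts of the plan use the timing of epinephrine.

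- Section 3, H1: "Early administration of intramuscular epinephrine reduces the risk of biphasic reactions and improves clinical outcomes".
- Section 2, first secondary objective: "To analyze independent risk factors for biphasic reactions, including delayed epinephrine administration, asthma history, and severity at presentation".
- Section 7, regression: "candidate variables: time to epinephrine, asthma, severity, multiple epinephrine doses".

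The supporting data item is in Section 6: "Treatments (IM epinephrine, time to first dose, number of doses, IV antihistamines, IV corticosteroids, fluid therapy, inhaled therapy". The source is given as "Data Sources: Patient files and electronic medical records (January 2014 – December 2024".

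A further secondary objective in Section 2 is descriptive: "To describe treatment patterns (use and timing of epinephrine, corticosteroids, antihistamines, fluids) in the emergency setting".

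The document gives no starting point for the time to first dose. It lists no symptom-onset time, ED arrival time, place of administration, or epinephrine given before arrival. It sets no cut-off for early or delayed, and does not say whether the model uses time as a continuous or a grouped variable.

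**The concern.** Section 1 describes anaphylaxis as developing rapidly, and H1 is a causal claim about treating that reaction early. The delay that bears on H1 runs from the start of the reaction to the first dose, wherever it was given. The plan neither says so nor collects the fields from which that interval could be built or checked.

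The setting is an ED, so counting from arrival is a plausible default. On that clock, a child who presents three hours after onset and is dosed within five minutes would count as early. If only ED doses were recorded, a child treated before arrival would count as late, or as untreated if no ED dose followed. Over an 11-year record period (2014 to 2024), different abstractors could also use different clocks.

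The stake is how H1 is read. Section 9 expects the results to guide practice. A null or reversed association on the wrong or a mixed clock could be taken as evidence that early epinephrine makes no difference, when that delay had not been measured. An undefined origin could also be settled after the data have been seen.

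**Working it through.** **Plan's own figure.** There is none to reproduce. The documents state no sample size, event count, effect size or time distribution. Section 7 gives a 0.05 significance level and takes all eligible patients.

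**Reading check.**

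| Needed to measure delay from onset | In the documents? |
|---|---|
| Time origin for time to first dose | No |
| Symptom-onset time | No |
| ED arrival time | No |
| Epinephrine before arrival, with time and place | No |
| Rule for children treated before arrival | No |
| Statement that time runs from ED arrival | No |
| Statement that only ED doses count | No |

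The first five rows are the gap. The last two show that the plan does not commit to the wrong clock either.

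**Illustration 1: door-to-dose used in place of onset-to-dose.** All time inputs are assumed. Let A be onset-to-arrival and D door-to-dose, both log-normal, with T = A + D. A true odds ratio of 2.0 acts on a median split of T, with 4% risk in the early half. The late odds are 2 × 0.04/0.96 = 0.0833, so the late risk is 0.0833/1.0833 = 7.69%. The analysis instead splits D at its median. If a share q of the children with long D truly have long T, then, because both splits are at the median:

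- risk in the long-D half = q × 0.0769 + (1 − q) × 0.04
- risk in the short-D half = (1 − q) × 0.0769 + q × 0.04

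With medians of 30 min for A and 10 min for D, simulation of 2 million children gives q = 0.62. The risks are 0.62 × 0.0769 + 0.38 × 0.04 = 0.0629 and 0.38 × 0.0769 + 0.62 × 0.04 = 0.0540. The observed odds ratio is (0.0629/0.9371)/(0.0540/0.9460) = 1.18.

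Other inputs, same method (log-SD 0.8 unless stated):

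| Median A (min) | Median D (min) | Log-scale correlation of A and D | Observed OR |
|---|---|---|---|
| 30 | 10 | 0 | 1.18 |
| 60 | 10 | 0 | 1.09 |
| 45 (log-SD 0.6) | 20 | 0 | about 1.27 |
| 30 (log-SD 0.6) | 30 | 0 | 1.47 |
| 15 | 30 | 0 | about 1.55 |
| 10 | 30 | 0 | about 1.65 |
| 30 | 10 | +0.3 | 1.30 |
| 60 | 10 | +0.3 | 1.23 |
| 30 | 10 | −0.3 | 1.05 |
| 60 | 10 | −0.3 | 0.97 |

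The range is about 1.0 to 1.65. Loss is greatest when most of the delay falls before arrival, and least when most falls in the ED. No pre-arrival dose enters this calculation.

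**Illustration 2: some truly early children recorded as late.** This is a separate error, again on assumed inputs: N = 300, two-sided 0.05, biphasic risk 5% early and 10% late (true odds ratio 2.11), and a share e truly early, of whom a share m are recorded as late. The observed late risk is [(1 − e) × 0.10 + e × m × 0.05] / [(1 − e) + e × m].

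For e = 0.6 and m = 0.4 this is (0.040 + 0.012)/0.64 = 0.08125, and the odds ratio is (0.08125/0.91875)/(0.05/0.95) = 1.68. Across e = 0.4 to 0.6, the observed odds ratio is 1.96 to 2.04 at m = 10% and 1.68 to 1.87 at m = 40%. Power falls from 34–39% with no error to about 16% at m = 40%. This assumes the error is unrelated to risk. If children treated before arrival differ in risk, the bias could go either way.

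**The case against.** The strongest reply is that the plan is silent here rather than wrong. Time to first dose is listed as a finished interval; its component clock times need not be listed, and it could be abstracted from charted onset. First dose and number of doses carry no ED restriction, so a charted pre-arrival dose could count. The reference to the emergency setting belongs to the descriptive objective and does not define the exposure for H1. The illustrations rest on assumed times, and the first applies only if door-to-dose is used. Onset may often be uncharted, in which case the gain shrinks to a definition and a stated limitation.

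Much of this stands. A reader might infer that H1 will be tested on door-to-dose time, or that children treated before arrival are classed as late or untreated. The documents support neither: no passage starts the clock at arrival (arrival time is not listed either), and no rule excludes earlier doses.

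What does not stand is that silence is harmless. Without the onset time and the place of the first dose, an analyst cannot rebuild the interval, tell which clock was used, or identify children treated before arrival. Those fields have to be abstracted while the charts are open.

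**Conclusion.** The point holds as an unspecified exposure, not as a demonstrated mismeasurement. The time origin and the handling of pre-arrival epinephrine are undefined, and the fields needed to settle them are not collected. It reaches H1, the delayed-epinephrine part of the first secondary objective, and the time-to-epinephrine term in the regressions. The primary objective, on observation time and on the frequency and timing of biphasic reactions, does not use this variable.

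The size is conditional. If door-to-dose stood in for onset-to-dose, a true odds ratio of 2.0 could appear anywhere from about 1.0 to 1.65, depending on the two interval distributions and their correlation, none of which the documents give. That range also assumes a median split, which the plan does not specify. It is a reason to fix the definition, not a forecast of the study's result. The point is a cheap improvement.

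**What to change.** **Section 6.** Add to the abstraction form:

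- symptom-onset time as charted, exact or in bands;
- ED arrival time;
- any epinephrine given before arrival for the same reaction, with its time and place (auto-injector, ambulance, referring hospital).

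**Section 7.** Define time to epinephrine, for analysis, as onset of the initial reaction to the first dose wherever given. Report door-to-dose separately as a process measure. State in advance how untreated children and missing onset times are handled, and add a sensitivity analysis that separates or excludes children treated before arrival. If onset time is missing in many charts, say that only door-to-dose was tested and limit the H1 conclusion to that.

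**Cost.** A few extra fields from charts already under review, and a short addition to the analysis plan. The downside is that onset times will be approximate or missing in some charts, so the H1 analysis set may be smaller.

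### With few biphasic events, the normality pre-test will often choose mean ± SD for onset time because the sample is small, and neither of its two summaries shows the late reactions

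*Combined protocol and SAP*

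**What the plan says.** The primary objective (Section 2) has two time quantities. One is the observation period: "To determine the average observation period in the pediatric emergency department". The other comes with the second half of the same objective, "to evaluate the frequency and timing of biphasic reactions". Neither is tied to a mean or a median.

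The choice is left to Section 7: "Continuous variables will first be tested for normality (e.g., Shapiro-Wilk test"). The consequence follows at once: "Normally distributed variables will be presented as mean \pm SD, while non-normally distributed variables will be expressed as median (IQR"). Group tests switch in the same way: "Student's t-test or Mann-Whitney U test for continuous variables, depending on distribution". Shapiro-Wilk is only an example, so the deciding test itself is not fixed. No separate level is given for it; the only level in the plan is the general 0.05.

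On size, the plan says "Sample size: All eligible patients". It gives no cohort size, biphasic rate or expected number of events. On onset times, the only information is the window in Section 1: "biphasic reactions (recurrence within 1–72 hours").

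**The concern.** A normality test that does not reject shows normality only if it had the power to reject. Onset time is recorded only in children who have a biphasic reaction, which may be a small group. In a small group Shapiro-Wilk has little power against skew. The rule then sends a skewed variable to mean ± SD because there are few events, and the summary of a primary quantity depends on sample size.

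Section 9 says the results should inform safe observation periods. For that purpose a reader needs to see when the late reactions occurred. Mean ± SD does not show this, and median (IQR) does not either.

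**Working it through.** The plan has no figure of its own to reproduce, so the check is a simulation of the rule in Section 7.

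**Inputs from the documents.** Onset lies within 1–72 h (Section 1). The rule is: not rejected gives mean ± SD, rejected gives median (IQR) (Section 7). The test level is 0.05, taking the general level to apply to the pre-test.

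**Assumptions.** Event count 5 to 30. Onset log-normal with median 8 h and log-SD 0.5, 0.8 or 1.0, truncated to 1–72 h. Shapiro-Wilk is the test used.

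**Step 1: how often the rule gives mean ± SD.** Percentage of samples with Shapiro-Wilk p ≥ 0.05, 20,000 draws per cell:

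| log-SD | 5 events | 8 | 10 | 15 | 20 | 30 |
|---|---|---|---|---|---|---|
| 0.5 | 89.9 | 81.1 | 75.8 | 60.9 | 47.5 | 27.9 |
| 0.8 | 83.5 | 64.6 | 53.5 | 31.2 | 17.2 | 3.9 |
| 1.0 | 79.9 | 57.1 | 43.8 | 20.6 | 8.5 | 1.0 |

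Over a wider set of seven right-skewed shapes (these three, a shifted exponential, gamma with shape 2 or 4, and log-uniform; 4,000 draws per cell) the ranges are 73–93% at 5 events, 30–86% at 10, 3–71% at 20 and 0–57% at 30. The top of each range is the mildest skew (gamma shape 4), where mean and median nearly agree (10.0 and 9.2 h). Normal data pass about 95% of the time, as they should.

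**Step 2: how different the answer is.** Samples of 10 events that pass the test:

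| log-SD | typical mean minus median | average mean + SD | average upper quartile | average largest time |
|---|---|---|---|---|
| 0.5 | 0.55 h | 13.1 h | 11.2 h | 16.5 h |
| 0.8 | 1.13 h | 17.1 h | 14.0 h | 22.8 h |
| 1.0 | 1.48 h | 19.9 h | 16.1 h | 27.2 h |

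The full assumed distribution at log-SD 1 has median 8.0 h, mean 12.0 h and SD 11.7 h. Its upper quartile is 15.4 h, mean + SD is 12.0 + 11.7 = 23.7 h, and the 95th percentile is about 37 h. Neither summary reaches the late times; the range and the individual values do.

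**Step 3: whole-cohort observation time.** It is measured in every child, so the sample is larger. With log-normal times (same median and limits) the pass rate at N = 50 is about 7% (log-SD 0.5) and under 1% (0.8). At N = 100 it is about 0.1% or less for both. For gamma shape 4 it is 29% at N = 50 and 3% at N = 100. At log-SD 0.3 it is still about 12% at N = 100, but there the mean exceeds the median by a factor of only exp(0.3²/2) = 1.046, under 5%.

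**Step 4: is a small event group plausible?** Events = N × rate. For assumed cohorts of 100 to 500 and assumed rates of 2% to 15%, this runs from 100 × 0.02 = 2 to 500 × 0.15 = 75. Ten or fewer is possible but not established.

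**The case against.** The strongest reply is that the harm is small and partly misplaced, and most of it stands.

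- **Event count and skew are assumed.** Eleven years of consecutive patients could yield enough events for the test to work. At log-SD 1 the problem is uncommon by 20 events and nearly gone by 30.
- **The samples that pass are those where the choice matters little.** A gap of 0.5–1.5 h would rarely change a reader's view.
- **A reader might infer that the pre-test itself hides the late tail.** It does not. Under the same model mean + SD reaches further than the upper quartile (about 20 h against 16 h at log-SD 1), so a forced median (IQR) alone would show less of the tail.
- **Mean ± SD might be said to imply impossible negative times.** At log-SD 1, mean minus 1.96 SD is below 0 h in 82–96% of passing samples of 5 to 15, but the plan proposes no such interval, and at log-SD 0.5 the share falls to 21–31%. Mean minus one SD is below 0 h in about 10% of passing samples at 5 events and under 1% at 10 (log-SD 1).
- **The main inferences are untouched.** The risk-factor hypotheses are addressed by logistic regression, which the pre-test does not govern. Raw times are collected (Section 6), so any summary can be recovered.

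Two things remain. The form of a primary summary is left to a low-powered test that is not even fixed, and no summary in the plan shows when the latest reactions occurred.

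**Conclusion.** The point holds as a minor, conditional one. With about 10 or fewer biphasic events and right-skewed onset times, the rule will often report mean ± SD because the sample is small, not because the data are normal. The weightier gap is that range and individual onset times are absent from both branches of the rule, and removing the pre-test alone would not close it.

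Two stronger readings should not be drawn. A reader might infer that the main observation-period result is at risk; in a cohort of about 100 or more it is little affected, since clear skew would be detected and weak skew makes little difference. A reader might also infer that the biphasic and non-biphasic groups will be given different summaries. Section 7 chooses by variable, not by group, and onset time does not exist in children without a biphasic reaction.

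The percentages rest on the assumed shapes, on Shapiro-Wilk being the test used, and on a 0.05 level.

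**What to change.** In Section 7, drop the normality pre-test for the time variables and state that:

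- ED observation time, time to first epinephrine and biphasic onset time are always summarised as median (IQR) and range; mean ± SD may be added;
- every biphasic onset time is listed individually;
- Mann-Whitney U is the group comparison for these times, whatever their distribution looks like.

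With this wording, the chance that onset time is shown only as mean ± SD is zero at any event count.

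The cost is a few lines of SAP text. If a variable is truly normal, Mann-Whitney has relative efficiency 3/π = 0.955, a loss of about 5%. A confidence interval for the median observation time is optional. Under normality the median has efficiency 2/π = 0.637, so the interval would be √(π/2) = 1.25 times as wide as one for the mean, about 25% wider.

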This study will provide evidence-based data for determining safe observation periods in pediatric anaphylaxis and will highlight risk factors for biphasic reactions in the Turkish pediatric population. Results are expected to guide clinical practice and support international guideline comparisons.

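### The primary biphasic-reaction frequency has no planned measure of precision, although the result is meant to inform how long children should be observed

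*Combined protocol and SAP*

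**What the plan says.** Section 2 makes the biphasic outcome a primary quantity: alongside the average observation time, the study is "to evaluate the frequency and timing of biphasic reactions". Section 1 gives the outcome window: "biphasic reactions (recurrence within 1–72 hours").

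Section 7 states how results will be summarised. For a yes/no outcome the rule is "Categorical variables will be summarized as n" with a percentage. The remaining items in that section are a normality check, summaries of continuous variables, two-group tests, logistic regression, and a p-value threshold below which a result is "considered statistically significant". On size it says "Sample size: All eligible patients", with no number. Section 4 gives the accrual window for the single centre: "Period: January 1, 2014 – December 31, 2024".

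Section 9 states the intended use: "evidence-based data for determining safe observation periods". It also expects the results to influence practice.

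**The concern.** The overall biphasic frequency is an estimate, and nothing in Section 7 attaches precision to it. The two-group tests and the logistic regression concern differences between children and predictors of the outcome. Neither gives an interval for the overall proportion, and the significance threshold has no bearing on it.

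This matters because of the use named in Section 9. When an event may be rare, the useful question for a statement on observation time is how high the risk could still be. A bare percentage does not answer that. A report of 0 (0%) shows the same percentage for 50 children as for 500, although the evidence differs greatly. At stake is a headline figure that looks firmer than the data allow.

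**Working it through.** **Inputs from the documents.** The outcome is binary and primary (Section 2). The planned summary is a count and percentage (Section 7). The number of children, the expected number of events and the target precision are not given, so the plan has no figure to reproduce. Every N, count and true rate below is an assumption used to show a range.

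**Step 1: zero events.** The exact (Clopper-Pearson) two-sided 95% upper limit for 0/N is 1 − 0.025^(1/N).

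- N = 50: 1 − 0.025^(1/50) = 7.11%
- N = 100: 1 − 0.025^(1/100) = 3.62%
- N = 200: 1 − 0.025^(1/200) = 1.83%
- N = 500: 1 − 0.025^(1/500) = 0.74%

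All four cases would be reported as 0 (0%).

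**Step 2: small counts.** For x events in N, the exact lower limit is the 2.5% quantile of Beta(x, N − x + 1). The upper limit is the 97.5% quantile of Beta(x + 1, N − x). The Wilson interval is a check.

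| Assumed count | Observed | Exact 95% CI | Wilson 95% CI |
|---|---|---|---|
| 2/100 | 2% | 0.24% to 7.04% | 0.55% to 7.00% |
| 5/100 | 5% | 1.64% to 11.28% | 2.15% to 11.18% |
| 10/100 | 10% | 4.90% to 17.62% | 5.52% to 17.44% |
| 4/200 | 2% | 0.55% to 5.04% | 0.78% to 5.03% |
| 10/200 | 5% | 2.42% to 9.00% | 2.74% to 8.96% |

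The two methods give nearly the same upper limits, so the choice between them is not critical.

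**Step 3: how easily a zero could arise.** The chance of no events at true risk p is (1 − p)^N.

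- p = 2%: 0.98^50 = 36.4%, 0.98^100 = 13.3%, 0.98^200 = 1.8%
- p = 1%: 0.99^50 = 60.5%, 0.99^100 = 36.6%, 0.99^200 = 13.4%

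At modest N, a zero count is quite compatible with a real risk of 1% to 2%. Reactions beginning after a given hour are a subset of all biphasic reactions, so a zero is at least as likely there.

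**Step 4: the denominator for late onset.** Suppose no late reactions are recorded among 100 children, but only 50 have records reaching the time point. The limit based on those 50 is 7.11%, not 3.62%. Counting all 100 would treat children who had already left as known to be free of a reaction.

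**The case against.** The strongest reply is that this is a gap in reporting and not a flaw in the analysis. The sentence in Section 7 is a generic rule for all categorical variables. It does not name the biphasic outcome and does not rule out an interval. If n and N are published, any reader can compute the overall interval; no data are hidden and no estimate changes. That stands, and it limits the weight of the point. It does not remove it: this is the only rule that covers a primary estimate, and following it produces no interval. For late onset, readers could work out an interval only if counts by time point and their denominators were published, which the plan does not require.

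A reader might go further and infer that the plan would declare a period safe because no reaction was seen after some hour. The documents do not support that. Section 7 contains no cut-off in hours, no late-onset proportion and no decision rule. If timing is recorded as a continuous variable, the stated rule gives a mean or median with its spread. Section 9 speaks of evidence and does not claim proof.

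A reader might also infer that at N = 100 the upper limit is always more than twice the estimate. It is at 5/100 (11.28/5 = 2.26) but not at 10/100 (17.62/10 = 1.76). At 10/200 the ratio is 9.00/5 = 1.80.

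Finally, it is tempting to let the upper limit settle the question of observation time. It cannot. The study is a chart review, the outcome window runs to 72 hours, and no contact after discharge is described. Readmission is collected, which may catch some returns. If late reactions are missed, the computed limit is too low.

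**Conclusion.** The point holds as a cheap and worthwhile improvement. A primary proportion, intended to inform observation periods, has no planned measure of precision. The size depends on N and the event count, which the documents do not give. Over the assumed range, a zero count leaves an upper limit from 7.1% at N = 50 down to 0.74% at N = 500. An observed 5% in 100 children is compatible with 1.6% to 11.3%.

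These figures assume independent children, one count per child and complete ascertainment of the outcome. They describe sampling error only. The point does not make the planned analyses invalid, and it does not show that the investigators intend a safety claim from a zero count.

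**What to change.** In Section 7, add that the biphasic frequency will be reported as n/N with a two-sided 95% confidence interval. Name one method, exact (Clopper-Pearson) or Wilson, and state that the upper limit will be given if the count is zero.

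If proportions with late onset are to be reported, list the time points before analysis. Define the denominator for each as children whose records cover that time point, and give the 95% interval.

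Add that any statement on observation periods will be interpreted in light of the upper limit, with the caveat that it does not account for reactions missed after discharge. This sets no clinical threshold.

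The cost is a few sentences and one table column for the intervals. No new data are needed for the overall interval; late-onset denominators need the time to which each child's record runs, which the observation and stay durations already listed in Section 6 should largely supply. The downside is that the headline result will look less certain.

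### The adjusted biphasic-reaction model has no safeguard if events are few: an odds ratio may then be infinite, and a Wald p-value, if used, uninformative

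*Combined protocol and SAP*

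**What the plan says.** Section 7, Regression analysis, plans "Logistic regression to identify independent predictors of biphasic reactions and prolonged observation (candidate variables: time to epinephrine, asthma, severity, multiple epinephrine doses". The method carries no qualification: no penalised or exact version, no choice between Wald and likelihood-ratio tests, no type of interval, no minimum number of events and no check for separation.

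The sample-size statement is "Sample size: All eligible patients", without a number or an expected event count. The patients come from one emergency department over the period "January 1, 2014 – December 31, 2024" (section 4). Section 1 notes that "Limited data exist from Turkey regarding pediatric anaphylaxis triggers, treatment practices, biphasic reaction frequency, and risk factors", and section 2 makes the frequency of biphasic reactions something the study is to estimate.

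The one provision for sparse data is Fisher's "exact test for categorical variables", in the Comparisons bullet, which concerns unadjusted comparisons. The software is SPSS v20.0.

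The adjusted model serves the secondary objective "To analyze independent risk factors for biphasic reactions, including delayed epinephrine administration, asthma history, and severity at presentation" and the biphasic parts of the hypotheses, for example H2, "A history of asthma and severe initial clinical presentation are associated with higher risk of biphasic reactions and prolonged observation requirements", and H3, "Children requiring multiple doses of epinephrine are at increased risk for hospitalization and biphasic reactions".

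**The concern.** Ordinary maximum likelihood breaks down when a predictor is present in all, or in none, of the cases (separation). The likelihood keeps rising as the coefficient grows, so no finite odds ratio exists and the printed value depends only on when iteration stops. The standard error grows faster than the coefficient, so a Wald p-value moves towards 1.

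This can happen precisely where an association is strongest. H2 and H3 expect biphasic reactions to concentrate among severe and multiple-dose children. If every case fell in such a group, the plan would yield no reportable adjusted odds ratio, and a Wald test would call the predictor non-significant. A remedy chosen after seeing this would be a data-driven choice.

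**Working it through.** The plan states no sample size, event count or power, so there is no figure to reproduce. Every input below is an assumption except the four candidate predictors, the 0.05 level and the 11-year window.

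**1. What separation does to one table.** Suppose 10 of 60 severe and 0 of 140 non-severe children have a biphasic reaction.
- Ordinary odds ratio: infinite; Wald p above 0.99.
- Likelihood ratio: null log-likelihood 10 ln(0.05) + 190 ln(0.95) = −39.70; fitted 10 ln(1/6) + 50 ln(5/6) = −27.03; chi-square 2 × 12.67 = 25.3, p = 0.0000005.
- Fisher p = 0.000003.
- Firth odds ratio (10.5 × 140.5)/(50.5 × 0.5) = 58.4, profile 95% CI 7.3 to about 7,600, p = 0.000002.

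A second table (6 of 45 against 0 of 105) shows the dependence on iteration. The printed odds ratio is about 11,000 after 10 steps and 37,000,000,000 after 25, while Wald p goes from 0.56 to 0.999. On the same data likelihood-ratio p is 0.0001.

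**2. How often separation occurs.** For one binary predictor with prevalence q among E events, the chance that one level is empty is (1−q)^E + q^E. At q = 20% this is 33%, 11% and 1% for E = 5, 10 and 20; at q = 10% it is 59%, 35% and 12%.

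For the full model I used simulation: intercept, standardised time with no effect, and asthma, severity and multiple doses each with odds ratio 2. There were 3,000 runs per cell (1,500 if N > 400). Ranges are over event rates of 3, 5 and 10%, and data sets with zero events count as failures.

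| Prevalence of asthma / severe / multiple doses | 5 events | 10 | 15 | 20 | 30 |
|---|---|---|---|---|---|
| Base: 20 / 30 / 12.5% | 44–50% | 10–12% | 2–3% | 0.3–0.9% | 0–0.1% |
| Common: 30 / 50 / 30% | 35–37% | 6–8% | 1.1–1.4% | 0.1–0.3% | 0–0.1% |
| Rare: 10 / 15 / 5.6% | 73–77% | 39–46% | 20–24% | 10–12% | 2.4–3.1% |

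A separate simulation with fixed event counts and slightly different inputs gave 52–55% at 4 events, 8–9% at 10 and at most 0.5% at 20.

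**3. What 20 events would require.** Cases per year = events / rate / 11. At rates of 3, 5, 10 and 15%, 20 events need 667, 400, 200 and 133 complete-record cases, or about 61, 36, 18 and 12 a year.

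**4. A strong predictor.** Severity odds ratio 8, 5% event rate, base prevalences, 4,000 runs per cell:

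| Power for severity | N = 100 | 200 | 300 | 400 |
|---|---|---|---|---|
| Wald | 20% | 63% | 87% | 95% |
| Likelihood ratio | 53% | 77% | 91% | 97% |
| Firth, penalised likelihood ratio | 45% | 76% | 91% | 97% |
| Fisher, unadjusted (separate runs) | 56% | 89% | 98% | 99% |

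Firth was significant and Wald was not in 25.4, 12.9, 3.8 and 1.5% of runs. In 22.7, 11.2, 3.4 and 1.3% this was because every case was severe.

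**5. Error rate, and a moderate effect.** With no severity effect, type I error at the same four N was 1.6/3.2/3.6/4.9% for Wald, 7.0/6.3/5.4/6.0% for the likelihood ratio and 3.4/4.6/4.4/5.4% for Firth. At severity odds ratio 2, power was 6/15/22/28%, 13/17/22/28% and 9/16/22/28%. The median ratio of upper to lower confidence limit, ordinary (non-separated runs) against Firth, was 66 v 69, 19 v 17, 10.8 v 10.3 and 7.6 v 7.4.

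**6. Prolonged observation.** The plan gives no cut-off, so exposure cannot be judged. With base prevalences and 100 children, separation was 46, 12, 0.3 and 2.0% if 5, 10, 25 and 50% were prolonged. Two sets of runs gave 7–9% at 60% of 100 and 5–7% at 50% of 80. The risk is not governed by the size of the smaller group: an uncommon predictor can fall wholly within a large prolonged group.

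**The case against.** **Nothing shows that events will be few.** This stands. A reader might infer that the planned model will fail; the documents do not support that. They give no case numbers or event rate, and the annual numbers in step 3 may or may not be reached. What remains is that the plan does not say what happens if they are not.

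**The plan names no Wald test.** This also stands. A reader might infer Wald p-values from the choice of SPSS, but section 7 specifies no test, so the power loss in step 4 rests on a second condition. The missing finite odds ratio does not.

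**Fisher's test is already planned and would flag a strong signal.** Largely true: its power in step 4 is at least that of adjusted Firth. But it is unadjusted and cannot show that a predictor is independent. Among runs where Firth was significant and Wald was not, Fisher was significant in 94, 98 and 98% at N = 100, 200 and 300. A reader might take these as the share of strong signals detected; they describe the discordant runs only.

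**A likelihood-ratio test recovers the power without an add-on.** True for the p-value. It still gives no finite estimate, and it was somewhat liberal at the smallest event counts (7.0% at N = 100).

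**The evidence on power is narrow.** It is: one event rate and one predictor profile. A material gain over Wald appears only at odds ratio 8 with N of 200 or less. It would be wrong to infer that Firth cures low power; at odds ratio 2 it hardly changes power or precision.

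**Conclusion.** The gap is real but conditional, and I would class it as a change to consider. The adjusted biphasic model has no safeguard against separation. Under the assumed inputs the risk is material at about 10 events or fewer, and up to about 30 if predictors are rare. With base or common predictors it is negligible from about 20 events.

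The main loss is an adjusted odds ratio that cannot be reported, together with a misleading p-value if Wald tests are used. This bears on the secondary objective on independent risk factors and the biphasic parts of H1 to H3. It leaves the descriptive primary objective untouched. Prevalences, event rates and effect sizes are all assumed; the plan supplies none of them.

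**What to change.** Add to section 7:

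> The biphasic model will be fitted by Firth penalised logistic regression with profile penalised-likelihood 95% CIs and p-values (no Wald p-values). Total biphasic events, and events in each predictor category, will be reported beside each odds ratio; results are exploratory and a wide interval will not be reported as no association. The same method will be used for the prolonged-observation model, or at least whenever any predictor-by-outcome cell is empty or the ordinary fit shows separation.

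The condition for the second model is tied to empty cells because, as step 6 shows, group size is a poor guide.

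The cost is these sentences and probably an SPSS add-on or a second package; no new data are needed. Shrinkage is slight: mean Firth log odds ratio 1.93 against a true 2.08 at 5 expected events, and 2.05–2.08 from 10. With plentiful events the results nearly coincide with the ordinary fit.

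If no add-on is feasible, a lesser fallback is ordinary logistic regression with likelihood-ratio p-values, reporting a separated predictor as not estimable. That gives no finite estimate.
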